6.4 Dose Selection/Modification

Dose Selection

The rationale for selection of doses to be used in this trial is provided in Section 4.0 – Background and Rationale. Details on preparation and administration of pembrolizumab (MK-3475) are provided in the Package Insert.

Dose Modification (Escalation/Titration/Other)

Adverse events (both non-serious and serious) associated with pembrolizumab exposure may represent an immunologic etiology. These adverse events may occur shortly after the first dose or several months after the last dose of treatment. Pembrolizumab must be withheld for drug-related toxicities and severe or life-threatening AEs as per Table 4 below. See Section 6.8.1 for supportive care guidelines, including use of corticosteroids.

Table 4. Dose Modification and Toxicity Management Guidelines for Immune-related AEs Associated with Pembrolizumab

General instructions:

1. Corticosteroid taper should be initiated upon AE improving to Grade 1 or less and continue to taper over at least 4 weeks.
2. For situations where pembrolizumab has been withheld, pembrolizumab can be resumed after AE has been reduced to Grade 1 or 0 and corticosteroid has been tapered. Pembrolizumab should be permanently discontinued if AE does not resolve within 12 weeks of last dose or corticosteroids cannot be reduced to ≤ 10 mg prednisone or equivalent per day within 12 weeks.
3. For severe and life-threatening irAEs, IV corticosteroid should be initiated first followed by oral steroid. Other immunosuppressive treatment should be initiated if irAEs cannot be controlled by corticosteroids.

Immune-related AEs	Toxicity grade or conditions (CTCAEv4.0)	Action taken to pembrolizumab	irAE management with corticosteroid and/or other therapies	Monitor and follow-up
Pneumonitis	Grade 2	Withhold	
 Administer corticosteroids (initial dose of 1-2 mg/kg prednisone or equivalent) followed by taper 	
 Monitor participants for signs and symptoms of pneumonitis Evaluate participants with suspected pneumonitis with radiographic imaging and initiate corticosteroid treatment Add prophylactic antibiotics for opportunistic infections
	Grade 3 or 4, or recurrent Grade 2	Permanently discontinue		

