Hypothyroidism	Grade 2-4	Continue	
 Initiate thyroid replacement hormones (eg, levothyroxine or liothyroinine) per standard of care 	
 Monitor for signs and symptoms of thyroid disorders.
Nephritis and Renal dysfunction	Grade 2	Withhold	
 Administer corticosteroids (prednisone 1-2 mg/kg or equivalent) followed by taper. 	
 Monitor changes of renal function
	Grade 3 or 4	Permanently discontinue		
Myocarditis	Grade 1 or 2	Withhold	
 Based on severity of AE administer corticosteroids 	
 Ensure adequate evaluation to confirm etiology and/or exclude other causes
	Grade 3 or 4	Permanently discontinue		
All other immune-related AEs	Intolerable/persistent Grade 2	Withhold	
 Based on type and severity of AE administer corticosteroids 	
 Ensure adequate evaluation to confirm etiology and/or exclude other causes
	Grade 3	Withhold or discontinue based on the type of event. Events that require discontinuation include and not limited to: Gullain-Barre Syndrome, encephalitis		

	Grade 4 or recurrent Grade 3	Permanently discontinue		

1. Withhold or permanently discontinue pembrolizumab is at the discretion of the investigator or treating physician.
 
NOTE: For participants with Grade 3 or 4 immune-related endocrinopathy where withhold of pembrolizumab is required, pembrolizumab may be resumed when AE resolves to \leq Grade 2 and is controlled with hormonal replacement therapy or achieved metabolic control (in case of T1DM).
				

Dosing interruptions are permitted in the case of medical / surgical events or logistical reasons not related to study therapy (e.g., elective surgery, unrelated medical events, patient vacation, and/or holidays). Subjects should be placed back on study therapy within 3 weeks of the scheduled interruption, unless otherwise discussed with the Sponsor. The reason for interruption should be documented in the patient's study record.

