 - For **Grade 3-4** events, treat with intravenous corticosteroids for 24 to 48 hours.
 - When symptoms improve to Grade 1 or less, a steroid taper should be started and continued over no less than 4 weeks.

- **Renal Failure or Nephritis:**
 - For **Grade 2** events, treat with corticosteroids.
 - For **Grade 3-4** events, treat with systemic corticosteroids.
 - When symptoms improve to Grade 1 or less, steroid taper should be started and continued over no less than 4 weeks.
- **Management of Infusion Reactions:** Signs and symptoms usually develop during or shortly after drug infusion and generally resolve completely within 24 hours of completion of infusion. Table 5 below shows treatment guidelines for subjects who experience an infusion reaction associated with administration of pembrolizumab (MK-3475).

Table 5. Infusion Reaction Treatment Guidelines

NCI CTCAE Grade	Treatment	Premedication at subsequent dosing
Grade 1 Mild reaction; infusion interruption not indicated; intervention not indicated	Increase monitoring of vital signs as medically indicated until the subject is deemed medically stable in the opinion of the investigator.	None
Grade 2 Requires infusion interruption but responds promptly to symptomatic treatment (e.g., antihistamines, NSAIDS, narcotics, IV fluids); prophylactic medications indicated for <=24 hrs	
Stop Infusion and monitor symptoms. Additional appropriate medical therapy may include but is not limited to:
 
 IV fluids Antihistamines NSAIDS Acetaminophen Narcotics 
Increase monitoring of vital signs as medically indicated until the subject is deemed medically stable in the opinion of the investigator. If symptoms resolve within one hour of stopping drug infusion, the infusion may be restarted at 50% of the original infusion rate (e.g., from 100 mL/hr to 50 mL/hr). Otherwise dosing will be held until symptoms resolve and the subject should be premedicated for the next scheduled dose.
 
Subjects who develop Grade 2 toxicity despite adequate premedication should be permanently discontinued from further trial treatment administration.
	
Subject may be premedicated 1.5h (\pm 30 minutes) prior to infusion of pembrolizumab with:Diphenhydramine 50 mg po (or equivalent dose of antihistamine).
 
Acetaminophen 500-1000 mg po (or equivalent dose of antipyretic).

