9.0.2 Clinical Procedures/Assessments

9.0.2.1 Adverse Event (AE) Monitoring

The investigator or qualified designee will assess each subject to evaluate for potential new or worsening AEs as specified in the Trial Flow Chart and more frequently if clinically indicated. Adverse experiences will be graded and recorded throughout the study and during the follow-up period according to NCI CTCAE Version 4.0 (see Section 11.2). Toxicities will be characterized in terms regarding seriousness, causality, toxicity grading, and action taken with regard to trial treatment.

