11.0 ASSESSING AND RECORDING ADVERSE EVENTS

An adverse event is defined as any untoward medical occurrence in a patient or clinical investigation subject administered a pharmaceutical product and which does not necessarily have to have a causal relationship with this treatment. An adverse event can therefore be any

unfavorable and unintended sign (including an abnormal laboratory finding, for example), symptom, or disease temporally associated with the use of a medicinal product or protocol-specified procedure, whether or not considered related to the medicinal product or protocol-specified procedure. Any worsening (i.e., any clinically significant adverse change in frequency and/or intensity) of a preexisting condition that is temporally associated with the use of pembrolizumab is also an adverse event.

Progression of the cancer under study is not considered an adverse event.

All adverse events that occur after the consent form is signed but before treatment allocation/randomization must be reported by the investigator if they cause the subject to be excluded from the trial, or are the result of a protocol-specified intervention, including but not limited to washout or discontinuation of usual therapy, diet, placebo treatment or a procedure.

From the time of treatment allocation/randomization through 30 days following cessation of treatment, all adverse events must be reported by the investigator. Such events will be recorded at each examination on the Adverse Event case report forms/worksheets. The investigator will make every attempt to follow all subjects with non-serious adverse events for outcome.

11.0.1 Definition of an Overdose for This Protocol and Reporting of Overdose to the Sponsor and to Merck

For purposes of this trial, an overdose of pembrolizumab will be defined as any dose of 1,000 mg or greater (≥ 5 times the indicated dose). No specific information is available on the treatment of overdose of pembrolizumab. Appropriate supportive treatment should be provided if clinically indicated. In the event of overdose, the subject should be observed closely for signs of toxicity.

If an adverse event(s) is associated with (“results from”) the overdose of pembrolizumab, the adverse event(s) is reported as a serious adverse event, even if no other seriousness criteria are met.

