FATSI: FATSI negative. PET: Probability of early termination at completion of first stage enrollment. α : Probability of false positive finding (type 1 error, falsely rejecting the null hypothesis).

Protocol Version: 15

We will analyze the paraffin embedded tumors of the participating patients for FA functional deficiency. Analysis will be conducted in batches.

We will report the 90% confidence interval estimates of iORR both overall and by FATS1 status using the exact method (Clopper-Pearson). We note, however, that the planned study is too small for a well-powered comparison given that we expect only 12 FATS1-negative patients. Instead, variation in iORR by FATS1 status will be assessed by considering the one-sided 95% lower confidence limit (95%LCL) for the difference. The following table illustrates the 95%LCL for several possible study outcomes in which iORR is higher in FATS1- patients. Taking the second rows as an example, an observed increase in iORR for FATS1-negative patients of 34.3%, based on 5 out of 12 FATS1- responders compared with 2 out of 27 FATS1+ responders, provides 95% confidence that the true increase for patients with FA deficient tumors is at least 9.4%, suggesting that further study of Pembrolizumab in FA deficient patients is warranted.

Table 11:

iORR					
FATS1-		FATS1+		Difference	95%LCL
5 / 12	41.7%	1 / 27	3.7%	38.0%	13.8%
5 / 12	41.7%	2 / 27	7.4%	34.3%	9.4%
5 / 12	41.7%	3 / 27	11.1%	30.6%	5.1%
4 / 12	33.3%	1 / 27	3.7%	29.6%	6.5%
4 / 12	33.3%	2 / 27	7.4%	25.9%	2.1%
4 / 12	33.3%	3 / 27	11.1%	22.2%	-2.3%

The incidence of severe (NCI CTCAE v4 grade 3+) adverse events or toxicities will be described. Kaplan-Meier curves will be used to estimate the distributions of overall survival and immune-related progression-free survival (iPFS). Point estimates and 2-sided 95% confidence intervals will be reported for selected times using Greenwood's variance and the log-log transform method. This will include the 20-week iPFS for purposes of comparison with the literature.

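### Section 12's only safety analysis is grade 3+ incidence, so lower-grade events for which pembrolizumab is withheld or stopped fall outside the planned safety summary

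*Combined protocol and SAP*

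**What the plan says.** The statistical plan in Section 12.0 states the safety analysis in one sentence: "The incidence of severe (NCI CTCAE v4 grade 3+) adverse events or toxicities will be described". Neither the objectives (Section 3) nor the endpoints (Section 5.3) include a safety item. Sections 12.1 (expansion cohort) and 12.2 (correlative data) add no safety summary.

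Data collection is much wider. Section 9.0.2.1 says "Adverse experiences will be graded and recorded throughout the study and during the follow-up period according to NCI CTCAE Version 4.0", and then "Toxicities will be characterized in terms regarding seriousness, causality, toxicity grading, and action taken with regard to trial treatment". Section 11.0 requires that, through 30 days after treatment ends, "all adverse events must be reported by the investigator". Section 11.0.4 has every change of grade within an episode recorded, and its Table 9 asks about drug relationship and whether the event led to discontinuation.

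The treatment rules act below Grade 3. In Table 4 (Section 6.4) the pneumonitis row stops drug permanently at "Grade 3 or 4, or recurrent Grade 2". The row for other immune-related events withholds at "Intolerable/persistent Grade 2". A general instruction, not tied to a grade, adds: "Pembrolizumab should be permanently discontinued if AE does not resolve within 12 weeks of last dose". For infusion reactions, Table 5 (Section 6.8.1) says: "Subjects who develop Grade 2 toxicity despite adequate premedication should be permanently discontinued from further trial treatment administration".

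Section 7.2 expects 39 patients assessable for tumor response and toxicity. It replaces patients whose drug is stopped for an acute hypersensitivity reaction during the first administration.

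**The concern.** The grade cut-off in the analysis does not match the cut-offs the protocol uses to interrupt or end treatment. An event serious enough, under the protocol's own rules, to take a patient off drug can sit below the threshold for the only safety figure the plan commits to.

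Two further features narrow that figure. It has no stated denominator, so it is open whether patients treated and then replaced are counted. It is also silent on causality, so a reader could not tell how much of a grade 3+ rate was attributed to the drug, even though attribution is recorded for each event.

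What is at stake is the tolerability half of the result. The trial aims to show a response rate of 20% against 5%. A reader weighing that activity would want to know how often toxicity interrupted or ended treatment, and the plan as written does not commit to reporting it.

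**Working it through.** The plan states no toxicity rate and no precision target for safety, so it has no figure to reproduce on this point. The check sets the analysis sentence against the treatment rules.

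**1. Events below Grade 3 that change treatment**

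| Source | Event | Level below Grade 3 | Action | In a grade 3+ incidence? |
|---|---|---|---|---|
| Table 4 | Pneumonitis | Grade 2 | Withhold | No |
| Table 4 | Pneumonitis | Recurrent Grade 2 | Permanent stop | No |
| Table 4 | Diarrhea/colitis | Grade 2 | Withhold | No |
| Table 4 | AST/ALT or bilirubin | Grade 2 | Withhold | No |
| Table 4 | Hypophysitis | Grade 2 | Withhold | No |
| Table 4 | Nephritis/renal | Grade 2 | Withhold | No |
| Table 4 | Myocarditis | Grade 1 or 2 | Withhold | No |
| Table 4 | Other immune-related | Intolerable or persistent Grade 2 | Withhold | No |
| Table 4, general instruction 2 | Any listed event | Unresolved at 12 weeks, no grade given | Permanent stop | Only if it reached Grade 3 |
| Table 5 | Infusion reaction | Grade 2 despite premedication | Permanent stop | No |

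Seven Table 4 categories withhold drug below Grade 3. Grade 1 appears only for myocarditis. The only grade-specific permanent stop below Grade 3 in Table 4 is recurrent Grade 2 pneumonitis. Grade 2 thyroid events are not in the list, because Table 4 continues drug for them.

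**2. Possible size**

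The documents give no rate for these events, so the rates q below are assumptions. With n = 39 (Sections 7.2 and 12.0), the expected number is n × q and the chance of at least one affected patient is 1 − (1 − q)^n.

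- q = 5%: 39 × 0.05 = 1.95, about 2 patients; 1 − 0.95^39 = 0.865.
- q = 10%: 39 × 0.10 = 3.9, about 4 patients; 1 − 0.90^39 = 0.984.
- q = 20%: 39 × 0.20 = 7.8, about 8 patients; 1 − 0.80^39 is above 0.99.

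Adding the 10 expansion patients gives n = 49 and expected numbers of 2.5, 4.9 and 9.8. Each affected patient is 1/39 = 2.6% of the main cohort. None would be counted unless the event worsened to Grade 3.

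**3. The denominator**

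Suppose, for illustration, that one patient has a Grade 3 hypersensitivity reaction at the first infusion and is replaced, and that no other grade 3+ event occurs. Counted over the 39 who were not replaced, the incidence is 0/39 = 0%. Counted over everyone given drug, it is 1/40 = 2.5%. The sentence in Section 12 does not say which applies, so the grade 3+ figure itself depends on an unstated choice.

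**The case against.** The strongest reply is that nothing is hidden. All grades are recorded, with causality and action taken. Serious events and events of clinical interest are reported whatever their grade (Section 11.0.3). The sponsor monitors aggregated safety data (Section 11.0.3.3), and regulatory reporting covers all adverse events (Section 11.0.5). The sentence in Section 12 does not say that grade 3+ is all that may be reported, and a wider table could be added when results are written up. The trial is also a small single-arm activity study of a marketed drug, with no safety objective, and no stopping rule, sample size or efficacy test rests on this sentence.

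Most of that stands, and it limits the point. The gap is in the specified analysis, not in the data. But collection, oversight and regulatory reporting are not a planned summary of the trial's result, and a table added later is discretionary.

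A reader might go on to infer several stronger things that the documents do not support:

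- That a patient stopped for recurrent Grade 2 pneumonitis would be reported as free of toxicity. A grade 3+ incidence says only that the patient had no grade 3+ event.
- That the count is inflated by cancer progression. Section 11.0 excludes progression from adverse events. Other events unrelated to the drug could still be counted.
- That the protocol names immune-related events as the drug's main harm. Section 6.4 says only that adverse events may have an immunologic cause.
- That an upper confidence limit from a zero grade 3+ count would measure the omission. It would describe grade 3+ events only.

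**Conclusion.** The point holds as a gap in the planned analysis. The one safety figure in Section 12 leaves out events below Grade 3 for which the protocol withholds or permanently stops pembrolizumab. It makes no use of collected causality and action-taken data, and it leaves the denominator open.

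The size cannot be derived from the documents. Under assumed rates of 5% to 20%, about 2 to 8 of 39 patients would have a treatment-limiting event that the planned summary does not count. The conclusion itself needs no assumed rate; it follows from setting Section 12 beside Tables 4 and 5. That replaced patients would be left out is a possibility, because neither Section 7.2 nor Section 12 says so.

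This should be changed but is not critical. The primary endpoint, the two-stage rule and the efficacy conclusions are unaffected, and no change to any clinical rule is implied.

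**What to change.** In Section 12, keep the grade 3+ incidence and add descriptive per-patient summaries. The denominator is every patient given any pembrolizumab, including those replaced under Section 7.2 after a first-infusion reaction and those in the expansion cohort (which can be shown in its own column). The summaries are:

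1. Immune-related adverse events by type and worst grade, all grades, with the Table 4 categories as the types.
2. Grade 3+ adverse events, treatment-related as well as all-cause.
3. Adverse events of any grade leading to withholding, and to permanent discontinuation, of pembrolizumab, including infusion reactions handled under Table 5.

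The cost is a few lines of wording and one extra output table. No visits, patients or dosing rules change. One check is needed: Table 9 in Section 11.0.4 asks only about discontinuation, so dose holds rely on the action-taken item in Section 9.0.2.1. The sponsor should confirm that the case report form captures a hold and links it to the event that caused it.

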12.1 Expansion Cohort

At the conclusion of the accrual as specified above, an expanded cohort of 10 patients with the diagnosis of metastatic or recurrent endometrial carcinoma or endometrial sarcoma will be enrolled. These patients need tissue availability and documentation of microsatellite low or stable. (see Section 6.1.1 for inclusion/exclusion criteria). All clinical benefit measure parameters and correlates will be obtained, as per the other patient. No additional statistical inferences, other than comparison between FATS1 positives and negatives in terms of clinical outcome will be done.

Protocol Version: 15

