Endometrium	1	12	13	7.7
Prostate	1	12	13	7.7
Adenoca unknown primary	2	8	10	20.0
Neuroendocrine	3	6	9	33.3
Mesothelioma	2	5	7	28.6
Cervical	0	5	5	0
Thymic	2	3	5	40.0
Sarcoma	1	2	3	33.3
Melanoma	2	1	3	66.7
Gastro-intestinal stromal tumor	1	2	3	33.3
Stomach	1	2	3	33.3
Small bowel	2	1	3	66.7
Appendix	1	1	2	50.0
Renal	1	1	2	50.0
Adrenal	1	1	2	50.0
Testicular	1	0	1	100.0
Vulva	0	1	1	0
Penile	0	1	1	0
Fallopian	0	1	1	0
Peritoneal	1	0	1	100.0
Hepatic	0	1	1	0
Total	185	458	643	28.7

We also showed that it is safe to administer the PARP inhibitor veliparib at doses up to 300 mg per day to patients with FA deficient tumors, and that veliparib can be safely combined with the DNA damaging agent mitomycin C. Activity was seen for the combination in heavily pretreated patients [17]. However, veliparib as a single agent, outside of BRCA/RAD51 germline mutated breast cancer did not show a substantial level of clinical activity. Potential reasons for this discrepancy would include: 1- veliparib is a weak PARP-trapping agent [18,19]; 2- restoration of FA functionality as a result of systemic treatment received between the time of tissue collection and enrollment in the trial [20-23]; or 3- the presence of additional mutations to which the repair deficient cell has become addicted (non-oncogenic addiction/induced-essentiality) [24-25].

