4.3 Preclinical and Clinical Trial Data for Pembrolizumab

Refer to the Investigator's Brochure for Preclinical and Clinical data.

4.4 The Interplay between DNA repair deficiency and Immune Checkpoint inhibition.

Le et al. recently reported a phase 2 study evaluating the clinical activity of pembrolizumab, in 41 patients with progressive metastatic carcinoma with or without mismatch-repair deficiency (26). The immune-related objective response rate and immune-related progression-free survival rate were 40% (4 of 10 patients) and 78% (7 of 9 patients), respectively, for mismatch repair-deficient colorectal cancers and 0% (0 of 18 patients) and 11% (2 of 18 patients) for mismatch repair-proficient colorectal cancers. The median progression-free survival and overall survival were not reached in the cohort with mismatch repair-deficient colorectal cancer but were 2.2 and 5.0 months, respectively, in the cohort with mismatch repair-proficient colorectal cancer.

Interestingly, patients with mismatch repair-deficient non-colorectal cancer had responses similar to those of patients with mismatch repair-deficient colorectal cancer (immune-related objective response rate, 71% [5 of 7 patients]; immune-related progression-free survival rate, 67% [4 of 6 patients]). Whole-exome sequencing revealed a mean of 1782 somatic mutations per tumor in mismatch repair-deficient tumors, as compared with 73 in mismatch repair-proficient tumors ($P=0.007$), and high somatic mutation loads were associated with prolonged progression-free survival ($P=0.02$). Since somatic mutations have the potential to encode "non-

self" immunogenic antigens the authors hypothesized that tumors with a large number of somatic mutations due to mismatch-repair defects may be susceptible to immune checkpoint blockade.

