Albumin	$\geq 2.5 \text{ mg/dL}$
Coagulation	
International Normalized Ratio (INR) or Prothrombin Time (PT)	$\leq 1.5 \times$ ULN unless subject is receiving anticoagulant therapy as long as PT or PTT is within therapeutic range of intended use of anticoagulants
Activated Partial Thromboplastin Time (aPTT)	$\leq 1.5 \times$ ULN unless subject is receiving anticoagulant therapy as long as PT or PTT is within therapeutic range of intended use of anticoagulants

^aCreatinine clearance should be calculated per institutional standard.

8. Female subject of childbearing potential should have a negative urine or serum pregnancy within 72 hours prior to receiving the first dose of study medication. If the urine test is positive or cannot be confirmed as negative, a serum pregnancy test will be required.
9. Female subjects of childbearing potential (Section 5.7.2) must be willing to use an adequate method of contraception as outlined in Section 5.7.2 – Contraception, for the course of the study through 120 days after the last dose of study medication.
10. Male subjects of childbearing potential (Section 5.7.1) must agree to use an adequate method of contraception as outlined in Section 5.7.1- Contraception, starting with the first dose of study therapy through 120 days after the last dose of study therapy.

Note: For 9 and 10, abstinence is acceptable if this is the usual lifestyle and preferred contraception for the subject.

6.1.1 Expansion Cohort.

Ten (10) additional subjects with the diagnosis of metastatic or recurrent endometrial carcinoma will be enrolled in the trial at the conclusion of regular enrollment with subject with the eligibility discussed in 6.1., and as per Sample size Calculation and Statistics Section (Section 12). The following will be necessary criteria for this expansion cohort.

1. Diagnosis of Endometrial Carcinoma or Sarcoma which is metastatic and has failed standard treatment or is recurrent, or for which standard chemotherapy is contraindicated or refused by patient.
2. Sufficient tissue is available for correlative studies as specified on Section 9.0.2.8.
3. MSI studies have been performed, either by immunohistochemistry or next generation sequencing and results show that patient is MS low or stable.
4. Patient meet all the inclusion criteria discussed above on 6.1 and none of the exclusion criteria discussed below on section 6.2.

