9. Has active autoimmune disease that has required systemic treatment in the past 2 years (i.e. with use of disease modifying agents, corticosteroids or immunosuppressive drugs). Replacement therapy (e.g., thyroxine, insulin, or physiologic corticosteroid replacement therapy for adrenal or pituitary insufficiency, etc.) is not considered a form of systemic treatment.
10. Has immunohistochemically proven mismatch repair deficient cancer (this test is standard in our center for colorectal and endometrial cancer patients, and documentation will be required to be negative to accept outside referrals with colorectal or endometrial cancer for this trial).
11. Has a history of (non-infectious) pneumonitis that required steroids or current pneumonitis
12. Evidence of interstitial lung disease.
13. Has an active infection requiring systemic therapy.
14. Has a history or current evidence of any condition, therapy, or laboratory abnormality that might confound the results of the trial, interfere with the subject's participation for the full duration of the trial, or is not in the best interest of the subject to participate, in the opinion of the treating investigator.
15. Has known psychiatric or substance abuse disorders that would interfere with cooperation with the requirements of the trial.
16. Is pregnant or breastfeeding, or expecting to conceive or father children within the projected duration of the trial, starting with the pre-screening or screening visit through 120 days after the last dose of trial treatment.
17. Has received prior therapy with an anti-PD-1, anti-PD-L1, or anti-PD-L2 agent.
18. Has a known history of Human Immunodeficiency Virus (HIV) (HIV 1/2 antibodies).
19. Has known active Hepatitis B (e.g., HBsAg reactive) or Hepatitis C (e.g., HCV RNA [qualitative] is detected).
20. Has received a live vaccine within 30 days of planned start of study therapy.

Note: Seasonal influenza vaccines for injection are generally inactivated flu vaccines and are allowed; however intranasal influenza vaccines (e.g., Flu-Mist®) are live attenuated vaccines, and are not allowed.

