7.2 Subject Replacement Strategy

We anticipate enrollment of 39 patients for which tumor and toxicity assessments following pembrolizumab administration can be made. We will replace patients enrolled for which clinical trial discontinuation was performed prior to any administration of pembrolizumab or those for which pembrolizumab is discontinued due to acute hypersensitivity reactions during the first administration of pembrolizumab. An attempt will be made to assess tumor response in all enrolled patients as specified in the protocol. However, patients experiencing clinical deterioration after two doses of pembrolizumab, will be considered treatment failures and will count as tumor progression. These patients will not be replaced.

We are also expecting that 30% of the patients enrolled will be negative on the FATS1 assay, which will be conducted in batched analyses.

See section 6.1.1 and 12.0.1 for expansion cohort.

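### Does the FATSI comparison in the ten-patient endometrial expansion cohort (Section 12.1) need a stated method, and a statement of whether it is within the cohort or pooled?

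*Combined protocol and SAP*

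**What the plan says.** Section 12.1 enrols ten patients once main accrual is complete, collects the same outcome measures and correlates as for other patients, and closes with: "No additional statistical inferences, other than comparison between FATS1 positives and negatives in terms of clinical outcome will be done". Section 6.1.1 defines the cohort: "Diagnosis of Endometrial Carcinoma or Sarcoma which is metastatic and has failed standard treatment or is recurrent", or standard chemotherapy contraindicated or refused, with tumors microsatellite-low or stable. Section 7.2 refers to a Section 12.0.1 for this cohort. No such section exists, and 12.1 is plainly meant.

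Section 12.0 gives the methods for the main study: "We will report the 90% confidence interval estimates of iORR both overall and by FATS1 status using the exact method (Clopper-Pearson"). It then says that the expected 12 FATSI-negative patients are too few for a well-powered comparison, and that instead "variation in iORR by FATS1 status will be assessed by considering the one-sided 95% lower confidence limit (95%LCL) for the difference". Overall survival and immune-related progression-free survival get Kaplan-Meier estimates with 95% intervals. Section 5.3.2 calls the FATSI results exploratory for lack of power.

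On how many FATSI-negative patients to expect, Section 7.2 says for the trial: "We are also expecting that 30% of the patients enrolled will be negative on the FATS1 assay". Table 1 in Section 4.1 has this row for endometrial tumors (negative, positive, tested, percent negative): "Endometrium 1 12 13 7.7".

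**The concern.** The one inference that Section 12.1 names is the one that ten patients support least. Two analysts could follow the section and do different things: compare FATSI groups within the ten, or pool with the 39. Neither the endpoint nor the method is fixed.

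If Table 1 is a guide, there may be one FATSI-negative patient or none, and a within-cohort comparison could be empty. If the lower limit from Section 12.0 were carried over to so small a group, it could look far more convincing than the data are. The closing sentence could also be read as barring a confidence interval for the cohort's own response rate, which ten patients can supply. At stake would be an uninformative or misleading statement about FATSI status in endometrial cancer.

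**Working it through.** **Inputs.** Cohort of 10 (Section 12.1). Response 40% in FATSI-negative and 10% in FATSI-positive patients, 3:7 ratio (Section 12.0). Endometrial FATSI-negative rate 1/13 (Table 1). Main study 12 versus 27 (Table 11). The 5% level and the tests used in step 2 are my assumptions, since Section 12.1 names none.

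**1. The plan's own figure.** Table 11, 5/12 versus 2/27, unpooled Wald limit:
- difference = 0.4167 − 0.0741 = 0.3426
- SE = √(0.4167×0.5833/12 + 0.0741×0.9259/27) = 0.1510
- limit = 0.3426 − 1.645×0.1510 = 0.094, the stated 9.4%

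All six rows reproduce this way.

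**2. Power within the cohort.** Power is the sum of P(a)·P(b) over outcomes that reject, with a ~ Bin(n₋, 0.40) and b ~ Bin(10−n₋, 0.10).

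- Fisher at 4:6 rejects at (3,0), (4,0) and (4,1): 0.1536×0.5314 + 0.0256×(0.5314+0.3543) = 0.104.
- Fisher at 3:7 rejects at (3,0) and (3,1): 0.064×(0.4783+0.3720) = 0.054.
- An exact unconditional test (Boschloo) at 3:7 also rejects at (2,0) and (3,2): 0.054 + 0.288×0.4783 + 0.064×0.1240 = 0.200.

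| Negative:positive | Fisher, one-sided 5% | Boschloo, one-sided 5% |
|---|---|---|
| 1:9 | 0% | 15.5% |
| 2:8 | 6.9% | 13.0% |
| 3:7 | 5.4% | 20.0% |
| 4:6 | 10.4% | 10.7% |
| 5:5 | 5.5% | 19.2% |

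Fisher falls from 2.8% at 6:4 to 0% at 9:1. Boschloo's maximum type I error is 2.3% to 3.9% over the splits shown, so its higher power is not bought with excess error. Averaged over the random split, power is 5.8% (Fisher) or 14.9% (Boschloo) at 30% prevalence, and 1.2% or 8.3% at 1/13.

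The often-quoted floor of p = 0.10 with one FATSI-negative patient (1/10) is specific to Fisher. Unconditionally, 1/1 versus 0/9 has probability at most 0.1×0.9⁹ = 0.039.

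**3. How many FATSI-negative patients.** At 1/13 the expected number is 10/13 = 0.77. P(0) = (12/13)¹⁰ = 0.449, P(1) = 0.374, so P(at most one) = 0.823. At 30%, P(at most one) = 0.149. The 95% interval for 1/13 is 0.2% to 36%, over which P(at most one) runs from more than 99.9% down to 7.6%. Table 1 gives neither microsatellite status nor an endometrial sarcoma row, so the count cannot be pinned down.

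**4. Pooled reading.** SE of the difference at 40%/10%:
- main study: √(0.24/12 + 0.09/27) = 0.153
- pooled at 1/13: √(0.24/12.77 + 0.09/36.23) = 0.146
- pooled at 30%: √(0.24/15 + 0.09/34) = 0.137

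One-sided Fisher power is 53% at 12 versus 27, about 63% at 13 versus 36 and 66% at 15 versus 34. Pooling is feasible and helps modestly. It may mix FATSI status with histology, but endometrial patients can also be among the 39, since Section 6.2 item 10 provides for them: "documentation will be required to be negative to accept outside referrals with colorectal or endometrial cancer for this trial". The documents give no endometrial response rate from which to size any such effect.

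**5. Carrying over the Wald limit.** At 1/1 versus 1/9 the difference is 0.889, SE = √(0.1111×0.8889/9) = 0.1048, and the limit is 0.889 − 0.172 = +0.717, against a one-sided Fisher p of 2/10 = 0.20. The limit is unsafe at this size, but Section 12.1 does not prescribe it for this cohort.

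**6. What ten patients can give.** Exact 90% intervals: 2/10 gives 3.7% to 50.7%; 0/10 gives 0% to 1 − 0.05^(1/10) = 25.9%.

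**The case for a change.** The case for amending the text is that Section 12.0 calls 12 versus 27 too small to compare and turns to estimation, whereas Section 12.1 names a comparison in ten patients with no such caveat. One sentence could separate the cohort, give its response rate an interval and label any FATSI contrast as exploratory, at no cost in patients or decision rules.

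Part of this stands. The text does leave within-cohort or pooled open, and power on response is 20% or less under the two exact 5% tests tried, over the splits computed for each.

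The rest does not carry a change:
- The caveat already exists. Section 5.3.2 applies it to FATSI results generally, and Section 12.0 states it immediately before.
- The interval is not clearly barred. No additional inferences, coming straight after Section 12.0, reads naturally as none beyond the methods just set out, and Section 12.1 treats outcomes as for the other patients.
- The misleading Wald result depends on a method the section does not assign.
- Low power is not absence of information. Clinical outcome covers more than response: for progression-free status at the mismatch-repair figures in Section 4.4 (78% versus 11%, borrowed here as an assumption), Fisher power reaches 53% at 4:6.
- Forbidding a within-cohort comparison, rather than treating it as descriptive, is a preference.

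**Conclusion.** No change is needed. This is missing detail in an exploratory add-on, of a kind analysts fill sensibly: report the ten patients with the Section 12.0 methods, treat any FATSI contrast among them as descriptive, and keep the 39-patient difference as the main FATSI result. The pass rule of at least 4 responses belongs to the 39 and is untouched under either reading.

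The weakness is real but already disclosed. For 40% versus 10% at one-sided 5%, within-cohort power is at most about 10% with Fisher's test and about 20% with an exact unconditional test (splits 1:9 to 5:5). These ceilings rest on the plan's assumed rates and on tests the plan does not name. With FATSI-positive response at 5%, for instance, the Fisher maximum is 13.8%. The expectation of few FATSI-negative patients rests on 1 of 13 and is too imprecise to count as a separate defect. A sentence saying whether the comparison is within-cohort or pooled would be an optional courtesy to the reader, since no stated rule gives a wrong result without it.
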